Infections resulting from health-care complications are the greatest cause of morbidity and mortality in hospitalized patients in the US. [1] Urinary tract infection (UTI) is the most common health care complication following surgery. [2] Rates are high, causing longer hospital stays, readmissions, and antibiotic use. Rates at UCH are near 40%, high compared to the national standard. About 15% of post-op complications result in extended stays or readmissions and costly antibiotic treatments. These infections should be preventable with prophylaxis and pre-treatment protocols but there is no standard protocol at UCH for minimizing the risk of UTI infection. We propose a catheter management protocol in which the catheters are treated with betadine and then inserted while remaining protected within the plastic sleeve, reducing airborne/contact exposures to the catheter. Betadine is a topical antiseptic used in the prevention of infections. It is widely available and a cost-effective intervention. Similar aseptic protocols have been tested and implemented in other countries however we lag behind in having a systematic protocol for reducing the incidence of UTIs complications.[2-4] A study in rural-India found that antiseptic techniques were the best preventable measure for device-related infections.[5] Patients currently receive what will be considered standard of care intra-operative catheter placement which involves placement of catheter in a sterile field, drainage to a closed system and shortest possible duration of catheter placement. We hypothesize that the implementation of a controlled antiseptic protocol to inserting the urinary catheter will reduce UTI rates following surgery.

III. Preliminary Studies/Progress Report:

The Gynecologic Oncology service performs between 15-20 surgeries per week. There are 5 providers who would require training in the protocol. The providers all have similar practice patterns as they pertain to current standard of care catheter placement. Training would be relatively straight forward and protocol adherence is expected to be high. Adherence can be monitored on the service by the principle investigator. Faculty Mentors include [name] who is an assistant professor in the department of Obstetrics and Gynecology at the UCH. He serves as the Principal Investigator for the Gynecologic Oncology Group, a national research consortium. His research has focused on all gynecologic cancer sites and surgical improvements.

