c. Study Design and Research Method. We will conduct a single-site Randomized Control Trial (RCT) in order to examine the use of an aseptic protocol for catheter insertion during gynecologic oncology surgeries for quality improvement. This study will take place at the UCH inpatient surgical unit of gynecologic oncology. The catheter protocol for QI will be conducted in the operating room prior to surgery and will not increase prep time or operating room time. Follow-up will be conducted during standard outpatient care visits and will also not increase clinic use time.

The intervention in this study is a controlled aseptic pre-treatment protocol for catheter use in the operating room involving dipping the tip of the catheter into betadine prior to insertion and maintaining catheter in the sterile plastic sleeve during preparation, insertion and post-operatively to avoid excess exposure to the environment. The Physician performing the operation will be responsible for inserting the catheter. Patients with normal UA pre-surgery will be randomized 1:1 to one of two arms prior to surgery:

- 1) Aseptic protocol for catheter insertion using betadine treated catheter and maintaining plastic sleeve on catheter *or*
- 2) SOC catheter insertion in which catheter is inserted right out of package/non-treated catheter.

Prior to study initiation, the PI will train providers on the proper use of the protocol. Catheter insertion procedures will be documented in the operation note following surgery. Compliance will be measured by adherence to both betadine use and maintenance of plastic sleeve. Standard of care practices for infection control are to be conducted by providers on all participants. This includes: hand hygiene, inserting catheters for appropriate indications, remove catheters when no longer needed, maintain a close system keeping bag and tubing below the bladder.

We will collect general patient demographics to assure similarities between the randomized groups. These will include age, race/ethnicity, BMI, insurance type, diagnosis (reason for surgery), history of diabetes, menopausal status, and smoking status. MRN data will be collected in order to pull data directly into the OnCore data management system.

d. Study Procedures

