Additionally, there is and will remain practice variations in catheter placement. While we hope to find a difference despite these differences, it is possible that the intervention may give a false impression of improvement simply by focusing attention on a protocol. While it is difficult to remove confounding from any study, randomization and analysis adjustments will be used to reduce as much as possible.

VI. Data Analysis Plan:

This study will assess a population of patients undergoing extended surgery requiring catheter placement to be performed by the Gynecologic Oncology service. De-identified patient data will be collected into OnCore and exported to SPSS for data analysis. Initial summary statistics will be performed to report the distribution of the data, including variable means, medians, proportions and missing data.

An intent-to-treat analysis will be conducted. All participants receiving treatment per protocol will be included in the final analysis. If there are any participants who are randomized but do not receive the intended treatment, we will document the reasons for their being withheld treatment.

For the primary outcome measure of UTI rate at each of the time points (24 hours and 14 +/- 2 days), we will perform a test of binomial proportions for testing the null hypothesis of no difference between the treatment arms. Because we are performing tests at two time points, we will adjust for the multiple comparisons using Bonferroni's method.

We will also explore the association between treatment arms and other covariates (symptomatic and demographics factors) using bivariate methods. The particular analysis method for testing the association between them will depend on the distribution of the covariates. For example, symptomatic presentation variables (fever, pelvic pain, sense of urgency or dysuria, and antibiotic use) are categorical, and their association with treatment arm will be evaluated with a chi-square statistic.

For demographic variables, Student's *t*-test (for continuous variables) and chi-square tests (for categorical variables) will be used to compare the two treatment arms. Variables found to be significant in these bivariate analyses will be included in multivariable analysis using logistic regression. Logistic regression models will be used to identify significant independent predictors associated with UTI

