occurrence for each treatment arm. We will fit separate logistic regression models for UTI occurrence at the two time points. The logistic model will allow for control of study covariates simultaneously. A p-value of <0.005 will be used to demonstrate statistical significance. IBM SPSS version 23 will be used for all statistical analyses.

Secondary outcomes will include a cost-analysis of the two treatment protocols and a patient satisfaction query in regards to the catheter procedure.

- Cost-analysis: The cost-effectiveness of the interventions will be assessed using hospital stay, readmissions, clinic/ED visits, and antibiotic costs per patient during the study period. An estimate of patient care costs will be derived using standard cost data described in the literature. The two groups will be compared in terms of average cost of treatment with a 95% confidence interval using a Bayesian statistic.
- Satisfaction: Patient satisfaction with the catheter protocol will be measured using a Likert-like scale questionnaire. Responses between the two groups will be compared using a Mann-Whitney-Wilcoxon statistic.

VII. Summarized Knowledge to be gained:

This study aims to reduce the incidence of urinary tract infections in patients undergoing surgery on the Gynecologic Oncology service through an aseptic protocol for placement. Such quality improvement studies are needed to help reduce complication rates and health-care costs.

VIII. References:

1. Septimus, E.J. and J. Moody, *Prevention of Device-Related Healthcare-Associated Infections*. F1000Res, 2016. **5**.
2. Stephan, F., et al., *Reduction of urinary tract infection and antibiotic use after surgery: a controlled, prospective, before-after intervention study*. Clin Infect Dis, 2006. **42**(11): p. 1544-51.
3. Barbadoro, P., et al., *Catheter-associated urinary tract infection: Role of the setting of catheter insertion*. Am J Infect Control, 2015. **43**(7): p. 707-10.
4. Amine, A.E., M.O. Helal, and W.M. Bakr, *Evaluation of an intervention program to prevent hospital-acquired catheter-associated urinary tract infections in an ICU in a rural Egypt hospital*. GMS Hyg Infect Control, 2014. **9**(2): p. Doc15.
5. Singh, S., et al., *Surveillance of device-associated infections at a teaching hospital in rural Gujarat--India*. Indian J Med Microbiol, 2010. **28**(4): p. 342-7.

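### The plan declares intent-to-treat but states inclusion by receipt of treatment per protocol, so the primary analysis set is left open

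*Combined protocol and SAP*

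**What the plan says.** Section VI declares the principle and then the inclusion rule in consecutive sentences: "An intent-to-treat analysis will be conducted. All participants receiving treatment per protocol will be included in the final analysis". The next sentence deals with "participants who are randomized but do not receive the intended treatment, we will document the reasons for their being withheld treatment". It does not say whether these participants are analysed, or in which arm.

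Section IV.c defines adherence: "Compliance will be measured by adherence to both betadine use and maintenance of plastic sleeve". The same section describes the intervention as "maintaining catheter in the sterile plastic sleeve during preparation, insertion and post-operatively to avoid excess exposure to the environment", so the sleeve component extends past insertion. Section III gives no adherence figure, only an expectation: "Training would be relatively straight forward and protocol adherence is expected to be high".

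The primary test is a comparison of binomial proportions at 24 hours and at 14 +/- 2 days. On multiplicity, section VI says: "Because we are performing tests at two time points, we will adjust for the multiple comparisons", by Bonferroni's method. Neither the test nor the multiplicity rule names the set of participants it applies to.

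**The concern.** Under intent-to-treat, the sentence on receipt of treatment is unnecessary. Read as the rule for who is analysed, it contradicts the sentence before it. Two analysts could build different data sets from this paragraph and both report the result as intent-to-treat.

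If the sentence were used as a filter, the primary comparison would no longer be between the groups as randomised. Two features of this trial make it doubtful that the filter would be neutral:

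- The stated compliance measure describes the intervention procedure. The documents do not say how per-protocol status would be judged in the control arm, so exclusions could be unequal between arms.
- Part of the adherence (sleeve kept on post-operatively) becomes known only after randomisation and surgery. Section IV.e expects that the cover may cause some added irritation, and the adverse-event text lists irritation leading to early catheter removal. That is a plausible route to non-adherence in one arm only.

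The UTI difference could then be biased in either direction, depending on the UTI risk of those left out.

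**Working it through.** **The text.** The three sentences in section VI, side by side:

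| Sentence | Who is analysed |
|---|---|
| First | Everyone randomised, as assigned (the ordinary meaning of intent-to-treat) |
| Second | Those who received treatment per protocol |
| Third | Not stated; reasons are recorded for those not given the intended treatment |

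The third sentence is where an intent-to-treat plan would normally say that these participants stay in their assigned arm. Section IV.c (compliance) and the serious-adverse-event text (discontinuation from the study) do not say how such participants are analysed either.

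**The plan's own figure.** Section IV.b gives 100 per arm for 40% against 20%, alpha 0.05, power 0.84. With a two-sided, continuity-corrected comparison:

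- Mean rate (0.40 + 0.20)/2 = 0.30; null standard error √(2 × 0.30 × 0.70/100) = 0.0648.
- Alternative standard error √((0.24 + 0.16)/100) = 0.0632.
- Power = Φ[(0.20 − 0.01 − 1.96 × 0.0648)/0.0632] = Φ(0.996) = 0.840.

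The stated size reproduces. It contains no allowance for non-adherence or exclusions.

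**Bias if the second sentence is applied as a filter.** Assumptions, none of them from the documents except the 40%: no true effect, 40% UTI in both arms, a fraction *e* dropped from the intervention arm only, and a UTI rate *r* among those dropped. The rate among those kept is (0.40 − *e* × *r*)/(1 − *e*). For example, *e* = 0.10 and *r* = 0.60 gives (0.40 − 0.06)/0.90 = 37.8%, a spurious benefit of 2.2 points.

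| *r* | 5% dropped | 10% dropped | 20% dropped |
|---|---|---|---|
| 60% | 38.9% (benefit 1.1) | 37.8% (benefit 2.2) | 35.0% (benefit 5.0) |
| 40% | 40.0% (none) | 40.0% (none) | 40.0% (none) |
| 20% | 41.1% (harm 1.1) | 42.2% (harm 2.2) | 45.0% (harm 5.0) |

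**Type I error.** Exact binomial enumeration of the uncorrected pooled two-proportion z-test, two-sided level 0.05/2 = 0.025 at one time point, with 100 controls against 95, 90 or 80 intervention participants:

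| *r* | 95 kept | 90 kept | 80 kept |
|---|---|---|---|
| 60% | 0.0258 | 0.0316 | 0.0604 |
| 40% (no selective dropping) | 0.0241 | 0.0243 | 0.0249 |
| 20% | 0.0255 | 0.0316 | 0.0612 |

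The 100 against 100 reference is 0.0254. At 10% dropped the excess is 0.0316 − 0.0243 = 0.0073, about 0.7 percentage points.

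The two-sided figure mixes directions. At 10% dropped, the chance of falsely declaring benefit is 0.0266 when *r* = 60%, against 0.0123 without selective dropping. When *r* = 20% it falls to 0.0053, and most of the error is false harm.

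Section VI also prints "A p-value of <0.005 will be used to demonstrate statistical significance". If that were the threshold, *r* = 60% gives 0.0054, 0.0072 and 0.0164, against 0.0048, 0.0054 and 0.0049 without selective dropping.

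**Power.** Assume 10% of the intervention arm is non-adherent and has the control rate of 40%. The intervention rate with everyone analysed is 0.9 × 0.20 + 0.1 × 0.40 = 0.22. Continuity-corrected power at two-sided 0.05 is 0.743 with all randomised analysed and 0.816 with the non-adherent excluded. The choice of set therefore changes the chance of a positive result, which is why it should be settled before data are seen.

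**The case against.** The best defence is that the text is loose but not contradictory. The second sentence does not say that only those treated per protocol are included, the phrase could mean treated under this study, and "An intent-to-treat analysis will be conducted" has a standard meaning that could be taken to govern. The link from per-protocol treatment to the compliance measure in section IV.c is also an inference; the sentence on withheld treatment fits a cancelled or changed procedure at least as well as a sleeve that was not maintained. Section IV.c does describe the control procedure and requires insertion to be documented, so a control-arm deviation could be recognised. Finally, every figure for size rests on assumed rates, and 20% dropped sits poorly with the expectation of high adherence.

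Much of this stands. No one is expressly excluded, the adherence filter is one possible reading, and the figures are illustrations. But the charitable reading does not supply what is missing: nothing in the documents says that randomised participants who did not receive the intended treatment are analysed in their assigned arm. A description of the control procedure is not a per-protocol criterion. The analysis set stays open on any reading.

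It is also fair to say that one sentence does not settle missing outcomes. A rule for them would be a useful addition, but its absence does not undermine the correction.

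**Conclusion.** The concern holds and should be fixed. The declared principle and the stated inclusion rule are inconsistent, and the set for the primary test is not defined elsewhere. This conclusion rests on the text and needs no assumed rate.

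The practical size is unknown. Under the assumptions above, the distortion is negligible at 5% dropped or less, modest at 10%, and substantial only at 20%, where type I error reaches about 0.060 to 0.061 against a nominal 0.025. It vanishes if those dropped have the same UTI risk as the rest, and its direction cannot be known in advance.

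**What to change.** Replace the second sentence of that paragraph in section VI with:

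> All randomised participants will be included in the primary analysis in the arm to which they were randomised, regardless of treatment received or adherence.

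Keep the sentence on documenting reasons. If a per-protocol analysis is wanted, label it a sensitivity analysis and state adherence criteria for both arms. It would help to add a rule for missing UTI outcomes, including those of participants discontinued early. The point at which a participant counts as randomised should also be made consistent, since section IV.d places randomisation on the day of the procedure and section IV.e places it at consent.

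The cost is one replaced sentence, plus adherence criteria if the sensitivity analysis is kept. There is no statistical cost against the intent-to-treat analysis already declared. The lower power with non-adherent participants included is a consequence of that declared principle. No procedure, visit or sample size changes.

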IV. Project Design and Procedures.

- a. Performance Measurement.** The primary outcome is UTI within 14 +/- 2 days post-surgery. A UTI is defined as an infection in any part of your urinary system which may include the kidneys, ureters, bladder, and urethra. Most infections involve the lower urinary tract (bladder and urethra), and are treatable with antibiotics. If a UTI spreads to the kidney, it can become a more serious complication. Women are at a greater risk of developing a UTI than men are. Pre-operative antibiotics will be collected to determine if this directly affects the outcome of a UTI. Visits to the ED for urinary pain, incontinence, or fever will also be followed for determination of UTI. Participants will provide a urine sample 0-24 hours before surgery. The sample will be tested with a rapid urine analysis (UA) test. This measure was chosen so that study UAs results are not to be confused with standard UAs conducted with samples collected after catheter placement. Participants will be followed up by research staff ~24 hours post-surgery for a second UA test. A third UA will be conducted at the patients' post-op check. At follow-up visits, participants will also

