be assessed for symptoms of UTI since surgery by assessment of: urethral discomfort, suprapubic tenderness or pelvic pain, sense of urinary urgency, frequency or dysuria, fever, antibiotic use, and clinical and laboratory data suggesting infection (UA with +leukocyte esterase +/- nitrates, urine culture with $>10^5$ bacterial colony forming units per mL (CFU)). Asymptomatic bacteriuria will be considered a UTI for this study (defined as $>10^5$ CFU/mL on urine culture). Patients who are treated with antibiotics for UTI without laboratory data suggesting infection will be included in UTI group. For participants reporting ED visits prior to 14 +/- 2 day visit, ED reports will be obtained and an assessment will be made regarding the symptomatic UTI diagnosis. Those meeting these criteria will be followed with symptom and laboratory analysis. All positive UA test will be confirmed by laboratory analysis for final diagnosis. Results of +leukocyte esterase +/- nitrites will be considered abnormal. If a diagnosis of UTI does not exist in the patient chart outside of study, the patient's clinical picture will be evaluated independently by 2 separate care providers to determine if meeting criteria for UTI (symptomatic bacteriuria as defined above). If there is discrepancy a third provider will be the determining opinion. Participants meeting the primary endpoint (UTI) will be discontinued from the study following.

Secondary outcomes include: hospital length of stay, readmissions, antibiotic use at the time of surgery and post-surgery. Measures of UTI, and secondary outcomes will be collected from observation during study visits and from the patient medical charts., If closed drainage system was disrupted during placement (to back fill bladder intra-operatively), and method of catheter discontinuation ("fill and pull" versus "pull and void" methods) will be collected for comparison between the groups for analysis as a possible confounding variables.

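### The plan defines UTI over a 14-day window but tests rates at two time points, and does not say how a woman discontinued for an earlier UTI counts at 14 days

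*Combined protocol and SAP*

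**What the plan says.** Section IV.a (Performance Measurement) defines the outcome over a window: "The primary outcome is UTI within 14 +/- 2 days post-surgery". The same section has women at follow-up visits "be assessed for symptoms of UTI since surgery by assessment of" a list of symptoms and findings. It reviews emergency department reports from before the two-week visit, and it places women treated for UTI without laboratory evidence in the UTI group. It then says: "Participants meeting the primary endpoint (UTI) will be discontinued from the study following".

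Section VI (Data Analysis Plan) describes the test differently: "For the primary outcome measure of UTI rate at each of the time points (24 hours and 14 +/- 2 days", each compared between arms by a test of binomial proportions. It continues: "Because we are performing tests at two time points, we will adjust for the multiple comparisons using Bonferroni's method". The adjusted analysis follows the same split: "We will fit separate logistic regression models for UTI occurrence at the two time points".

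On the analysis population, section VI says "An intent-to-treat analysis will be conducted" and then "All participants receiving treatment per protocol will be included in the final analysis". Neither sentence assigns a 14-day outcome to a woman whose participation ended early because of a UTI.

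**The concern.** One outcome over a window and a rate at each of two visits are different quantities unless a rule links them. The discontinuation rule makes the difference matter. A woman positive on the 24-hour sample, or diagnosed on day 5, has no planned Visit 4. An analyst who builds the 14-day variable from visit data therefore has no two-week result for exactly the women who already had the outcome. Four treatments are open: event, non-event, missing, or out of the denominator.

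If these women are left out, the 14-day test compares only women who are still free of UTI. That group is selected after randomisation by an event the intervention is meant to prevent, so randomisation no longer protects the comparison. If they stay in the denominator as non-events, the rate counts only late UTIs. Neither version is the outcome in section IV.a. Left unwritten, the choice could be made after the data are seen, and it affects the primary result.

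**Working it through.** **Inputs.** From section IV.b: control UTI rate 40%, a 50% reduction (so 20%), 100 women per arm, alpha 0.05, power 0.84. From section VI: two tests with Bonferroni, so 0.05/2 = 0.025 each. Two-sidedness is assumed from the null of no difference. The share of UTIs found before Visit 4 is not in the documents, so it is varied.

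**Formula.** Continuity-corrected normal approximation for two proportions:

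power = Φ[(|p1 − p2| − ½(1/n1 + 1/n2) − z·s0) / s1]

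Here s0 = √[p̄(1 − p̄)(1/n1 + 1/n2)], s1 = √[p1(1 − p1)/n1 + p2(1 − p2)/n2], and p̄ is the pooled rate. z is 1.960 at 0.05 and 2.241 at 0.025.

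**The plan's own figure.** With 0.40 v 0.20 and 100 per arm, s0 = 0.0648 and s1 = 0.0632. Then (0.20 − 0.01 − 1.960 × 0.0648)/0.0632 = 0.996, and power is 0.840. This matches the stated 0.84. The sample size therefore corresponds to one two-sided test at 0.05 of one UTI proportion per arm. At 0.025 the same test has power 0.760.

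**Earlier cases dropped.** Hold the 14-day totals at 40 v 20 per 100 and let a share f be found early in both arms. The rates among those remaining are (40 − 40f)/(100 − 40f) and (20 − 20f)/(100 − 20f).

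Example, f = 50%: 20/80 = 25.0% v 10/90 = 11.1%, a difference of 13.9 points. The correction is ½(1/80 + 1/90) = 0.0118, p̄ = 30/170 = 0.176, s0 = 0.0586 and s1 = 0.0587. Then (0.1389 − 0.0118 − 1.960 × 0.0586)/0.0587 ≈ 0.209, and power is 0.583.

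| Share early | 14-day rates, earlier cases dropped | Power at 0.05 | Power at 0.025 |
|---|---|---|---|
| 0% (or earlier cases counted as events) | 40.0% v 20.0% | 0.840 | 0.760 |
| 10% | 36/96 = 37.5% v 18/98 = 18.4% | 0.808 | 0.720 |
| 25% | 30/90 = 33.3% v 15/95 = 15.8% | 0.745 | 0.645 |
| 50% | 20/80 = 25.0% v 10/90 = 11.1% | 0.583 | 0.471 |

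**Earlier cases kept as non-events.** At 50% early the rates are 20% v 10% with 100 per arm, and power at 0.05 is 0.43.

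**Effect entirely early.** Suppose 25 v 5 UTIs are found early and 15 v 15 later. With earlier cases dropped, the 14-day rates are 15/75 = 20.0% v 15/95 = 15.8%, and power at 0.05 is 0.076, although the totals are still 40 v 20. If all those early UTIs are found by 24 hours, the planned 24-hour test of 25% v 5% with 100 per arm has power 0.94 at 0.025.

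**The case against.** A reader might infer that the plan removes already infected women from the 14-day rate. No sentence says so. The outcome named in section VI is the primary outcome, which section IV.a defines over a window. The analysis is labelled intent-to-treat, no exclusion for earlier UTI is listed, and symptoms are assessed from surgery onward. Ending a woman's visits does not erase an endpoint already recorded. All of this stands: a cumulative 14-day rate is a fair reading. It is not the only one, because section VI speaks of rates and separate models at each time point. The intent-to-treat label does not settle it either. It says whom to analyse, not what outcome value a discontinued woman receives, and the per-protocol sentence after it pulls the other way.

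A reader might also infer that UTIs diagnosed between visits count nowhere. The documents do not support that. Section IV.a uses emergency department reports, chart diagnoses and antibiotic treatment to determine UTI, and Visit 4 in section IV.d reviews emergency visits since the previous visit. These provisions suggest that interval UTIs are meant to feed the 14-day outcome.

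Finally, one might conclude that an early benefit would be lost to the trial. The planned 24-hour test answers that for a large effect seen by 24 hours, as the 25 v 5 example shows. It gives less cover for smaller early effects or for UTIs found between 24 hours and Visit 4.

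**Conclusion.** The point holds as an inconsistency in the primary analysis. The outcome is defined over a window, it is tested and modelled at two time points, and the rule that ends participation at UTI leaves the 14-day numerator and denominator open. It does not hold as a claim that the plan excludes earlier cases.

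The size is conditional. If earlier cases count as events, the loss is zero. If they are dropped, it is small at 10% early (about 3 points of power at 0.05, 4 at 0.025) and large at 50% early (about 26 and 29 points). These figures rest on an assumed early share, equal in both arms. They also treat the 40% as a 14-day cumulative rate, although sections II and IV.b give it without a time window. Power at 0.025 is the fairer baseline if both time points remain primary. The 0.005 threshold stated after the logistic models in section VI was not used here. The bias from conditioning on a post-randomisation event does not depend on the power figures, but it arises only if earlier cases are dropped.

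**What to change.** In section VI, define the 14-day endpoint as any UTI by a qualifying route from catheter insertion through the day 14 +/- 2 visit. The routes are the 24-hour sample, an emergency department or chart diagnosis or treatment, and Visit 4. State that all randomised women form the denominator and that every earlier UTI is carried forward as an event, although study visits have ended. Use the same variable in the 14-day logistic model.

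Describe the 24-hour result as the early component of this endpoint and say whether it remains a primary test. With one test of the cumulative endpoint at 0.05, the stated 100 per arm and power of 0.84 stand. If both tests stay at 0.025, power at 14 days is 0.76, and 119 per arm would be needed for 0.84 (same formula).

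The definition itself costs a few sentences and one derived variable. It needs no new data or patients and no change to the discontinuation rule. It should be written before the outcome data are analysed by arm.
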